4.3 Exclusion Criteria

1. Has renal function of CrCl < 30 mL/min at time of enrollment. CrCl will be calculated using the Cockcroft-Gault equation using the most recently obtained and available serum creatinine value collected.
2. BIC/F/TAF is the only antiretroviral therapy ever used for treatment of HIV infection.
3. Is allergic to any of the HIV meds in BIC/F/TAF (bictegravir, emtricitabine, or tenofovir alafenamide).
4. Pregnant or breastfeeding.
5. Is currently taking dofetilide or rifampin.
6. Has severe hepatic impairment (Child-Pugh Class C).
7. ALT or AST $> 5 \times$ ULN.

4.4 Lifestyle Considerations

No lifestyle restrictions are required based on study procedures.

4.5 Screen Failures

Screen failures are defined as participants who consent to participate in the clinical trial but are not subsequently entered in the study. A minimal set of screen failure information is required to ensure transparent reporting of screen failure participants, to meet the Consolidated Standards of Reporting Trials (CONSORT) publishing requirements and to respond to queries from regulatory authorities. Minimal information includes demography, screen failure details, eligibility criteria, and any serious adverse event (SAE).

Individuals who do not meet the criteria for participation in this trial (screen failure) because of a renal function value exclusion may be rescreened. Rescreened participants should be assigned the same participant number as for the initial screening.

4.6 Strategies for Recruitment and Retention

The Renal Transplant Program works in close collaboration with the Transplant/Oncology Infectious Diseases Program, including clinical research trials. Recruitment will primarily rely on referrals from the Renal Transplant Program and/or existing patients of the infectious disease investigators. Recruitment will primarily be sources from outpatient clinics, such as the Infectious Disease Clinic and the Renal Transplant Clinic. The target enrollment is 20 subjects. Monthly enrollment logs will be collected.

Subjects will be compensated \$40 per outpatient visit, as a stipend to cover travel costs. For visits that require pharmacokinetic blood sampling, subjects will be compensated \$200 per outpatient visit, as a stipend to cover travel costs and time.

5. Registration Procedures

5.1 Subject Registration

Subjects will be registered within the WRG-CT as per the standard operating procedure for Subject Registration.

6. Study Procedures

Study procedures are outlined in the Schedule of Assessments (Section 6.1)

6.1 Schedule of Assessments*

Activity	D 1	D 3	D 8	D 15	D 22	W 4	W 8	W 12	W 16	W 24	W 32	W 36	W 48	FU – M3	FU – M6	UV ^k	
Visit Window (Days)	±1	±3				±7											
Informed consent	X ^a																
Inclusion/Exclusion Criteria	X																
Research study visit, including weight	X	X ⁱ	X ^j	X ^j	X ^j	X	X	X	X	X	X	X	X	X	X	X	
Physical exam	X					X ^b		X ^b		X		X ^b	X	X ^b	X ^b	X ^b	
Questionnaire booklet administration	X																
Questionnaire completion ^c						X		X		X		X	X	X	X	X	
Dispense study medication	X										X						
T-lymphocytes, HIV viral load	X					X		X		X		X	X	X	X	X	
HIV-resistance testing		As needed, as per investigator ^d															
Tacrolimus level	X	X ⁱ	X ^j	X ^j	X ^j	X	X	X	X	X	X	X	X	X	X	X	
BUN, creatinine		X ⁱ	X ^j	X ^j	X ^j	As needed, as per investigator ^e											
Clinical Safety Labs ^f	X					X	X	X	X	X	X	X	X	X	X	X	
TAF levels, intracellular (dried blood spot) ^g								X		X		X	X		X	X	
TAF levels, intracellular (PBMC) ^h								X									
Pharmacokinetics ⁱ								X									

Abbreviations: D = Day; W = Week; M = Month; FU = Follow-up; UV = Unscheduled Visit

*If services outside of the study (standard of care, or "SOC") are completed for a patient during the study period, only the research-related tests and procedures will be billed to the study. SOC tests and procedures are expected throughout the study period for this population.

^a Informed consent may be obtained up to 2 months before D1. Subjects enrolled into Group 2 will begin the study schedule at the Day 1 visit and will then be inserted into the Schedule of Assessments at the discretion of the Principal Investigator based on stability of the subject's HIV viral load and tacrolimus levels.

^b If there are complications, as deemed by the investigator, a physical exam will be conducted at this time point. If institutional restrictions limit outpatient visits, the most recent physical exam completed by the primary care physician will be used to avoid direct contact or exposure of patients.

^c Questionnaires may be completed by phone or returned by mail, if institutional restrictions limit outpatient visits.

^d HIV resistance testing will be performed if there are two consecutive breakthrough HIV viral loads >50 copies/mL, spaced 4-6 weeks apart.

^e Additional BUN and/or creatinine labwork may be drawn at these timepoints, if deemed necessary for safety purposes by the investigator.

^f Clinical Safety Labs include: CBC, complete metabolic panel, urinalysis, eGFR, urine protein/creatinine ratio, urine albumin/creatinine ratio, phosphorus, retinol binding protein, and beta 2 microglobulin. For subjects enrolled in Group 2, all standard of care lab values and concomitant medications will be collected for 60] days prior to the Biktarvy switch date and the duration of Biktarvy therapy will also be recorded.

^g Three samples will be collected on W12 at 0, 4, and 24 hours (the 24 hour time point is optional, if feasible), and 1 sample will be collected at visits W24, W36, and W48, and FU – M6. Stored samples will be sent to [name] at the University of Colorado's Antiviral Laboratory.

^h Three samples will be collected on W12 at 0, 4, and 24 hours (the 24 hour time point is optional, if feasible). Stored samples will be sent to [name] at the University of Colorado's Antiviral Laboratory.

ⁱ Six samples will be collected on W12 at 0, 0.5, 1, 2, 4, and 24 hours (the 24 hour time point is optional, if feasible). Pharmacokinetic testing for Group 2 subjects will be completed once the subject's tacrolimus levels are stable as per the Principal Investigator for 2-4 weeks.

^j The study visits and bloodwork at these timepoints will be optional, to be completed as needed, as per the investigator.

^k If a subject needs to stop treatment as per the Data and Safety Monitoring Plan (Section 12), the subject will be seen as soon as possible for an Unscheduled Visit and will continue to be followed for the duration of the study as per the Schedule of Assessments for non-terminated patients.

Informed consent will be obtained on Day 1 or up to 2 months prior to Day 1, before starting the study (switch day) (Section 6.1).

Patients will have bloodwork completed throughout the study, as shown in the Schedule of Assessments (Section 6.1).

Pharmacokinetic (PK) studies will be assessed at Week 12 when the renal function is stable (decided by PI). Intracellular TAF levels by dried blood spot will be collected during the Week 12 visit at 0, 4, and 24 hours post-dose (the 24 hour time point is optional, if feasible). Additionally, 1 sample will be collected at Week 24, Week 36, Week 48, Month 6 Follow-up. Over the course of the study, 7 dried blood spot collections will be completed per patient. Intracellular TAF levels by PBMC will be collected once during the Week 12 visit at 0, 4, and 24 hours post-dose (the 24 hour time point is optional, if feasible). An intensive pharmacokinetic day will take place at the Week 12 visit, during which up to 7 samples will be collected at 0, 0.5, 1, 2, 4 and 24 hours post-dose (the 24 hour time point is optional, if feasible). This bloodwork is outlined in Section 6.1. Bloodwork for the intracellular TAF level testing and pharmacokinetic testing will be stored and sent to [name] at the University of Colorado's Antiviral Laboratory. (14-16)

A health-related quality of life questionnaire (Appendix) will be administered to each patient to assess satisfaction with a one pill regimen as well as adverse events (Section 6.1).

If a subject needs to stop treatment as per the Data and Safety Monitoring Plan (Section 12), the subject will be seen as soon as possible for an Unscheduled Visit and will continue to be followed for the duration of the study as per the Schedule of Assessments for non-terminated patients.

If services outside of the study (standard of care, or "SOC") are completed for a patient during the study period, only the research-related tests and procedures will be billed to the study, regardless of study visit date overlap. SOC tests and procedures are expected throughout the study period for this population.

Sample Collection

Samples include plasma and peripheral blood mononuclear cells (PBMC). Blood is collected in EDTA tubes for plasma separation. CPT vacutainers are used to isolate PBMC, which are counted with an automated countess cytometer (Invitrogen™, Thermo Fisher Scientific Corporation, Carlsbad, CA) and lysed. BIC, F, and TAF in plasma are assayed using a validated LC/MS/MS methodology with a lower limit of quantification (LLOQ) of 10 ng/mL (16).

7. Study Intervention

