Short Title:	Switch to BIC/FTC/TAF after Renal Transplant
Clinical Phase:	IV
Principal Investigator:	[name]
Study Description:	Hypothesis: We hypothesize that BIC/F/TAF will be efficacious and safe in the management of HIV+ post renal transplant patients, and will have few adverse reactions and drug-drug interactions with tacrolimus in this population
Sample Size:	N = 20
Study Population:	Virally-suppressed HIV+ adults post-renal transplant
Enrollment Period:	November 2020 to May 2023
Study Design:	Single arm, open-label, switch study, following subjects for 48 weeks with a 6 month follow-up
Study Duration:	November 2020 – December 2024
Participant Duration:	In this single arm, open-label, switch study, we propose to switch virally suppressed HIV+ adults post-renal transplant to BIC/F/TAF and follow the subjects for 48 weeks with a 6 month follow-up (Section 6.1).
Study Agent:	BIC/F/TAF® (BIC/F/TAF)
Primary Objectives:	
 1. To determine the efficacy of BIC/F/TAF in HIV+ patients post renal transplant at 24 weeks and 48 weeks post-switch to BIC/F/TAF. 2. To assess the safety and tolerability of BIC/F/TAF in HIV+ patients post renal transplant at 24 weeks and 48 weeks post-switch to BIC/F/TAF. 3. To assess the pharmacokinetics of BIC/F/TAF in HIV+ patients post renal transplant and its interactions with immunosuppressive agents (Tacrolimus) at 12 weeks post-switch to BIC/F/TAF. 4. To assess renal biomarkers including urine protein/creatinine ratio; urine albumin/creatinine ratio; eGFR; serum BUN, creatinine and phosphorus; tacrolimus levels; retinol 2 binding protein and B2 microglobulin post renal transplant at 24 weeks and 48 weeks post-switch to BIC/F/TAF.
Secondary Objectives:	
 1. To assess the incidence of kidney graft rejection after switching to BIC/F/TAF post renal transplant at 24 weeks and 48 weeks post-switch to BIC/F/TAF. 2. To assess the immunologic activity (CD4 count/percentage) of BIC/F/TAF post renal transplant in conjunction with immunosuppressive agents (tacrolimus) at 24 weeks and 48 weeks post-switch to BIC/F/TAF. 3. To determine patient satisfaction with BIC/F/TAF post renal transplant by utilizing a questionnaire to assess health-related quality of life outcomes at 24 weeks and 48 weeks post-switch to BIC/F/TAF.

Primary Endpoints:

1. Proportion of subjects with plasma HIV-1 RNA <50 copies/ml at week 48.

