2. Safety and tolerability (monitoring and recording adverse events) in subjects who switched from a prior ARV regimen to BIC/F/TAF.
3. Pharmacokinetics of BIC/F/TAF and tacrolimus, including intracellular TAF levels (dried blood spot, PBMC).

Secondary Endpoints:

1. Changes from baseline in CD4+ T lymphocyte cell count/percentages post renal transplant.
2. Incidence of rejection rates of the kidney transplant post renal transplant and correlation with tacrolimus levels.
3. Patient satisfaction with reduced pill burden and adverse events with BIC/F/TAF.

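### As the schedule most naturally reads, the satisfaction form is first completed at week 4, after the switch, so no pre-switch score exists for a before/after comparison

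*Combined protocol and SAP*

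**What the plan says.** The Schedule of Assessments in Section 6.1 has two questionnaire rows. "Questionnaire booklet administration" is marked at Day 1 only. "Questionnaire completion" is marked at W4, W12, W24, W36, W48, the month 3 and month 6 follow-ups, and unscheduled visits. The Day 1 step is not defined. The text below the table says that consent is obtained "before starting the study (switch day"), which makes Day 1 the day of the switch.

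Sections 3.1 and 6.1 both say that the questionnaire "will be administered to each patient to assess satisfaction with a one pill regimen as well as adverse events".

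The third secondary objective in the synopsis begins "To determine patient satisfaction with BIC/F/TAF post renal transplant by utilizing a questionnaire" and names weeks 24 and 48 after the switch. The matching endpoint is "Patient satisfaction with reduced pill burden and adverse events with BIC/F/TAF". The CD4 endpoint in the same list is worded differently: "Changes from baseline in CD4+ T lymphocyte cell count/percentages post renal transplant".

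Section 3.1 also admits patients who switched before they were identified for the study (Group 2). Note a to the schedule adds: "Subjects enrolled into Group 2 will begin the study schedule at the Day 1 visit". These subjects are already on the study drug at that visit.

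**The concern.** This is a single-arm switch study, so the only available comparator for satisfaction is the same patient on the earlier regimen. If the form is first filled in at week 4, that comparator is never measured. A high mean score at week 24 or 48 could then mean that the switch improved satisfaction, or that these patients were already satisfied, and the data could not help tell the two apart.

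The week 4 form cannot serve as a baseline. The Appendix asks about current treatment and experience in recent weeks, and by week 4 both refer to BIC/F/TAF.

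The stake is limited to how the third secondary endpoint can be interpreted. Its wording about reduced pill burden invites a comparison with what patients took before, and the schedule as read supplies no data for one.

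**Working it through.** The plan gives no figure to reproduce here: the sample size rests on feasibility, and the analysis is descriptive. The check has two parts.

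**1. When is the form completed?**

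| Row in Section 6.1 | Visits marked |
|---|---|
| Booklet administration | D1 |
| Completion | W4, W12, W24, W36, W48, M3, M6, unscheduled |
| T-lymphocytes and viral load | D1, W4, W12, W24, W36, W48, M3, M6, unscheduled |

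The viral-load row has the same marks as the completion row plus Day 1. Section 12 lists the scheduled viral-load visits in words, and they agree with the table. The blank Day 1 cell in the completion row is therefore unlikely to be a column shift from text extraction.

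Scheduled completions: 5 on-study (W4, W12, W24, W36, W48) + 2 follow-up (M3, M6) = 7. Number before the switch: 0.

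Two features favour reading the Day 1 step as a hand-out. A separate completion row exists, and the note allowing completion by phone or mail is attached to that row alone.

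**2. What would a Day 1 form provide?**

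For n subjects with both a pre-dose form and a later form, the half-width of the 95% confidence interval for the mean change, in SDs of the change score, is t(0.975, n−1)/√n.

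| n pairs | Calculation | Half-width (SD of change) | Source of n |
|---|---|---|---|
| 20 | 2.093/4.472 | 0.468 | Synopsis; Section 4.6 |
| 18 | 2.110/4.243 | 0.497 | Section 3.1 |
| 15 | 2.145/3.873 | 0.554 | assumed |
| 10 | 2.262/3.162 | 0.715 | assumed |
| 5 | 2.776/2.236 | 1.242 | assumed |

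The first two rows assume no Group 2 subjects and no missing forms. The last three are illustrations, because the documents give neither the Group 2 number nor the expected form completion. The SD of the change is not given either, so the half-widths cannot be put on the scale of the questionnaire.

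The Appendix has nine items scored 0 to 6. If they are summed, the range is 0 to 9 × 6 = 54, but no scoring rule is stated. None of the nine items names pill burden.

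**The case against.** The strongest reply is that no stated aim requires a baseline. The objective concerns satisfaction with BIC/F/TAF at weeks 24 and 48. Section 2 gives the questionnaire's purpose as understanding patients' experience on the drug. Section 10.1 lists no satisfaction result among the expected outcomes. The authors wrote change from baseline for CD4 and did not write it here. Sections 2 and 2.1.2 present lower pill burden as a consequence of one-pill dosing, so the endpoint may simply describe the product. This stands: the point is a design improvement and not an internal contradiction, and the week 24 and 48 description is unaffected.

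Second, administration could mean completion, since Sections 3.1 and 6.1 use the verb for the act that assesses satisfaction. That reading is possible. It makes the separate completion row harder to explain, and it still leaves the Day 1 step undefined.

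Third, a Day 1 form would not isolate pill burden, because no item names it and an open-label before/after change also carries expectation. This is correct and limits the claim to overall satisfaction. It does not remove the value of knowing whether patients were already satisfied before the switch.

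Fourth, the synopsis gives enrollment as November 2020 to May 2023, and nobody already switched can supply a baseline. If enrollment is complete, only clarification and rewording remain.

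**Conclusion.** The concern holds. On the likelier reading of the schedule, 0 of 7 scheduled forms precede the switch, and a change in satisfaction from the earlier regimen cannot be estimated from prospectively collected scores. The effect is confined to the interpretation of one secondary endpoint.

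A pre-dose form would support a descriptive paired comparison with a half-width of 0.47 to 0.50 SD of the change score at best, and less precision for every Group 2 subject or missing form.

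The conclusion rests on two assumptions: that the Day 1 step is a hand-out, and that some comparison with the earlier regimen is wanted. The first is the better reading but not certain. The second is inferred from the endpoint's wording alone. The change is worth making because it is cheap and because a pre-switch score cannot be obtained later except by recall, which is weaker.

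**What to change.** - State in Section 6.1 what the Day 1 booklet step consists of.
- Mark questionnaire completion at Day 1, before the first BIC/F/TAF dose, for subjects not yet switched.
- For those subjects, report descriptively the change from Day 1 in overall treatment satisfaction at weeks 24 and 48, with a 95% confidence interval and the number of pairs. Name the score in advance, for example the nine-item sum (0 to 54).
- Report Group 2 as on-treatment scores only.
- State that no item names pill burden, so any change reflects the whole open-label switch and not pill count alone.
- If no baseline can be added, reword the endpoint as on-treatment satisfaction with BIC/F/TAF.

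The cost is one nine-item form at an existing visit where the booklet is already provided, one mark in the table, and a protocol amendment with IRB approval before implementation (Section 9.1). The gain depends on how many subjects remain to be switched, which the documents do not state. The rewording needs no new data.

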7.1 Study Intervention/Device Description

BIC/F/TAF is a three-drug fixed dose combination product containing 50 mg of bictegravir (BIC), 200 mg of emtricitabine (FTC), and 25 mg of tenofovir alafenamide (TAF). The recommended dosage of BIC/F/TAF is one tablet taken orally once daily with or without food in adults. BIC/F/TAF should be stored below 86°F (30°C).

7.2 Availability

BIC/F/TAF is an FDA-approved agent, to be supplied to investigators by Gilead.

7.3 Acquisition and Accountability

The investigator, or a responsible party designated by the investigator, will maintain a careful record of the inventory and disposition of all agents/device received from Gilead on a Drug Accountability Record Form.

8. Data Collection

The data collection plan for this study is to utilize REDCap to capture all treatment, toxicity, efficacy, and adverse event data for all enrolled subjects.

8.1 REDCap

REDCap (Research Electronic Data Capture) is a free data management software system that is fully supported by the Weill-Cornell Medical Center CTSC. It is a tool for the creation of customized, secure data management systems that include Web-based data-entry forms, reporting tools, and a full array of security features including user and group based privileges, authentication using institution LDAP system, with a full audit trail of data manipulation and export procedures. REDCap is maintained on CTSC-owned servers that are backed up nightly and support encrypted (SSL-based) connections. Nationally, the software is developed, enhanced and supported through a multi-institutional consortium led by the Vanderbilt University CTSA.

9. Regulatory Considerations

9.1 Institutional Review Board/Ethics Committee Approval

As required by local regulations, the Investigator will ensure all legal aspects are covered, and approval of the appropriate regulatory bodies obtained, before study initiation.

Before initiation of the study, the protocol, the ICF, other written material given to the patients, and any other relevant study documentation will be submitted to the appropriate Ethics Committee. Written approval of the study and all relevant study information must be obtained before the study center can be initiated or the IP is released to the Investigator. Any necessary extensions or renewals of IRB approval must be obtained for changes to the study, such as amendments to the protocol, the ICF, or other study documentation. The written approval of the IRB together with the approved ICF must be filed in the study files.

The Investigator will report promptly to the IRB any new information that may adversely affect the safety of the patients or the conduct of the study. The Investigator will submit written summaries of the study status to the IRB as required. On completion of the study, the IRB will be notified that the study has ended.

All agreed protocol amendments will be clearly recorded on a protocol amendment form and will

be signed and dated by the original protocol approving signatories. All protocol amendments will be submitted to the relevant institutional IRB for approval before implementation, as required by local regulations. The only exception will be when the amendment is necessary to eliminate an immediate hazard to the trial participants. In this case, the necessary action will be taken first, with the relevant protocol amendment following shortly thereafter.

Once protocol amendments or consent form modifications are implemented at the lead site, Weill Cornell Medicine, updated documents will be provided to participating sites, as applicable. Weill Cornell Medicine must approve all consent form changes prior to local IRB submission.

Relevant study documentation will be submitted to the regulatory authorities of the participating countries, according to local/national requirements, for review and approval before the beginning of the study. On completion of the study, the regulatory authorities will be notified that the study has ended.

9.2 Ethical Conduct of the Study

The Investigators and all parties involved should conduct this study in adherence to the ethical principles based on the Declaration of Helsinki, GCP, ICH guidelines and the applicable national and local laws and regulatory requirements.

This study will be conducted under a protocol reviewed and approved by the applicable ethics committees and investigations will be undertaken by scientifically and medically qualified persons, where the benefits of the study are in proportion to the risks.

